Another interaction with participants will be the debriefing experiences, where students will do a group debriefing. Afterward, participants in the hot debrief group will do their post-test immediately after their debrief on the same day as the simulation, and another post-test after 24 hours of the first post-test. And then, the cold debrief participants will do the simulation, wait 24 hours, have the debrief, and will do an immediate post-test, and another post-test after 24 hours of the first post-test. The simulation will be conducted in order to complete the BLS assessment checklist at baseline, post-test, and second post-test. The same simulation and BLS Assessment checklist will be conducted at baseline, post-test, and second post-test. The BLS competence and DES will be administered online via REDCap. During the qualitative phase, participants will engage in a focus group which will be the final interaction. Random sampling will be used to select subsamples from both hot and cold groups for the focus group..

6.3 Describe procedures being performed to monitor subjects for safety or minimize risks.

The study carries minimal risk. Potential participants will not be expected to expose more than what they might face in a simulation experience that they are familiar with. Participants will be informed that they can choose to participate or not and can withdraw at any time. They can also decline to answer any questions that make them uncomfortable. The PI will receive training from the Co-PI/Faculty Advisor to monitor participants for any psychological stress during study phases. The PI and Co-PI/Faculty Advisor will meet weekly to discuss interactions with participants and ensure that the procedures for managing data protect confidentiality.

6.5 Where applicable, list and describe the data collection tools such as surveys, data collection forms, etc. All tools described should be uploaded in the RAP Smart Form on the Local Site Documents page unless they are standardized, validated tools.

For Phase 1

- (A) Demographic
- (B) BLS Competence Checklist

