| | 
13.1 Describe the amount, method, and timing of payments to subjects.
 
13.0 COMPENSATION FOR SUBJECTS
 
Phase 1:
 
-Hot Debriefing Participants:
 
Day One (Baseline, Immediate Debriefing, Post-Test): \$25 Amazon gift card will be sent via email after completing baseline.
 
Second Post-Test (after 24 hours of the first post-test): \$20 Amazon gift card will be sent via email after completing second post-test.
 
-Cold Debriefing Participants:
 
Day One (Baseline): \$25 Amazon gift card will be sent via email after completing baseline.
 
Following Day (Debrief and Post-Test): \$25 Amazon gift card will be sent via email after completing debrief and post-test.
 
Second Post-Test (after 24 hours of the first post-test): \$20 Amazon gift card will be sent via email after completing second post-test.
 
-Phase 2 (Qualitative Phase): \$25 Amazon gift card will be sent via email after completing the qualitative interview. Participants who choose to withdraw at anytime during the qualitative study will also receive a \$25 Amazon gift card will be sent via email.
 
Total for hot debriefing in phase 1 (\$45)
 
Total for cold debriefing in phase 1 (\$70)
 
Total of hot debriefing in phases 1 and 2 (\$70)
 
Total of cold debriefing in phases 1 and 2 (\$95)
 |

| | |
|--|--|
| | 
The cold debriefing group will need 3 days to complete phase 1, while hot debriefing will need only 2 days to complete phase 1.
 
Both the hot and cold debriefing groups have the same time for participation; however, the cold group will need to arrive 24 hours after the simulation experience. Participants in the cold group will require additional time for transportation and scheduling a different day for the research activity. Therefore, the PI will give an additional \$25 Amazon giftcard to compensate.
 |
|--|--|

| | |
|--|---|

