| 
14.0 WITHDRAWAL OF SUBJECTS
 | 
14.1 Describe the anticipated circumstances under which subjects will be withdrawn by the study team from the research without their consent.
 
Because this study presents a minimal risk, it is not anticipated that any potential participants will be withdrawn from the study. In case they feel uncomfortable or distressed in the study, they can stop, take a break, and re-join. Participants have the right to withdraw themselves from the study at any time and will never be persuaded to participate in research activities that they refuse. If participants refuse any part of the study, that data will be considered missing.
 
Study participants will be withdrawn by the study team without their consent if the study team cannot contact them to complete phase 1 of the study.
 
Participating to phase 2 is optional, if a participant completes Phase 1 but cannot be contacted to complete Phase 1, their Phase 1 data will not be deleted.
 |
| | 
14.2 Describe any procedures for orderly termination.
 
The participants have the liberty to withdraw from the study at any point, and the study team can also withdraw them if they cannot be contacted. Participants can inform the PI of their decision to withdraw verbally, via voicemail, or email. If the study team is unable to contact a participant, they may receive a voicemail stating that they have been withdrawn from the study due to non-contactability.
 |
| | 
14.3 Describe procedures that will be followed when subjects withdraw from the research, including partial withdrawal from procedures with continued data collection, withdrawal of previously collected data upon request, etc.
 
Potential participants have the right to withdraw themselves from the study at any time, and will never be persuaded to participate in research activities that they refuse. If potential participants refuse any part of the study, further data collection will be stopped, and that data will be considered missing. Previously collected data will be withdrawn upon request.
 |
| | |

TEMPLATE: RESEARCH PROTOCOL

| NUMBER | ACTIVE DATE | PAGE |
|---------|-------------|----------|
| HRP-503 | 02-04-2020 | 20 of 40 |

| | |
|--|--|

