| 17.0 DATA MANAGEMENT AND CONFIDENTIALITY | 17.1 Describe the data analysis plan, including any statistical procedures or power analyses. |
| | For quantitative phase 1, Statistical power G*Power 3.1 was used to determine sample size based on a 2-tailed, two-way repeated measure ANOVA for the design, a type I error of 0.05, a statistical power of 80% (type II error), and a large effect size of eta square .25-.99 (Faul et al., 2007). Based on the literature, a large effect size is appropriate for the use of simulation (Padilha et al., 2019; Pauly-O'Neill, 2009). Based on G*Power 3.1, the recommended sample size will be 26 participants in each group. Still, because there is a possibility that participants may withdraw from the study, the total number will be 30 participants in each group. There is a total of 183 eligible participants. |
| | 
Statistical Plan
 
The statistical analysis will be used by JMP Pro 16 software. The descriptive analysis for students' demographics will be computed to describe means, standard deviations, and frequencies. For hypothesis 1a, the appropriate statistical analysis test will be the repeated measure ANOVA to find the difference between the experimental and control group in pre and post-intervention. For hypothesis 1b, an independent t-test will be used to find the differences between the two groups in the BLS competence level. The p-value of <0.05 will be considered statistically significant, and the confidence interval will be set at 95%. If the p-value is less than 0.05, we will reject the null hypothesis; If the p-value is more than 0.05, we will fail to reject the null hypothesis. For hypothesis 2, an independent t-test will be used to compare means between hot debriefing and cold debriefing groups. DES with P-values <0.05 will be considered statistically significant.
 |

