# The Effect of Immediate Versus Delayed Debriefing on Basic Life Support Competence In Undergraduate Nursing Students.

NCT06624449

October 5, 2023

*[name] ([name])*

[Company Name] | [Company Address]

The statistical analysis was conducted using JMP Pro 16 software. Descriptive statistics for the students' demographics were calculated, including means, standard deviations, and frequencies. A Paired t-test was used to determine the differences between the experimental and control groups before and after the intervention. An independent t-test was applied to examine differences in BLS competence levels between the two groups. A p-value of less than 0.05 was considered statistically significant, with a 95% confidence interval. If the p-value was below 0.05, the null hypothesis would be rejected; if it exceeded 0.05, we would fail to reject the null hypothesis. Independent t-tests were also used to compare the mean debriefing experience scores between the hot and cold debriefing groups, with p-values below 0.05 considered statistically significant.

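### Refusing any one part ends all later data collection, and H1b is an unadjusted t-test on available scores although only the cold arm must return before its first post-test

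*Protocol*

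**What the plan says.** **Withdrawal.** Protocol 14.1 states: "Study participants will be withdrawn by the study team without their consent if the study team cannot contact them to complete phase 1". It also treats a refused part as missing and lets a distressed student pause and come back. Section 14.3 goes further: "If potential participants refuse any part of the study, further data collection will be stopped, and that data will be considered missing". It then says that data already collected are taken out if the student asks. Section 6.3 says of participants: "They can also decline to answer any questions that make them uncomfortable".

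**Retention.** The only sentence on keeping data is in 14.1. It begins with Phase 2 being optional, describes someone who completes Phase 1 but cannot be reached to complete Phase 1, and ends "their Phase 1 data will not be deleted".

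**Visits.** Under 6.2, the hot arm is debriefed and takes its first post-test on the day of the baseline simulation. The cold arm waits 24 hours before debriefing and first post-test. Section 13.1 confirms: "The cold debriefing group will need 3 days to complete phase 1, while hot debriefing will need only 2 days to complete phase 1". It pays the cold arm an extra $25 for the added trip.

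**Analysis.** Protocol 17.1 and the SAP both test H1b with an independent t-test. For the before-and-after question the SAP says: "A Paired t-test was used to determine the differences between the experimental and control groups before and after the intervention". Neither document names an analysis set, a baseline covariate, a missing-data method or a report of missing scores by arm. Section 11.2 allows 15% attrition overall, not split by arm.

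**The concern.** Two features combine.

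First, 14.3 turns a small refusal into a full stop. By the order in 9.1, the debriefing survey comes before the first post-test. Read literally, a student who declines only that survey gives no post-test at all, although willing to be assessed. Section 14.1 implies a narrower consequence, and 6.3 allows single questions to be declined, so staff could apply the rule differently from one student to the next.

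Second, the arms are not equally exposed to loss. A hot student who leaves after day one has a post-test score. A cold student who leaves after day one has none. The H1b t-test compares whoever has a score, without using the baseline score collected from both arms. If the cold students who fail to return differ in competence from those who do, the comparison is no longer between the groups as randomised. What is at stake is the trial's main between-arm comparison of BLS competence.

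**Working it through.** **Inputs from the documents.** 30 enrolled and 26 needed per group (3.1, 17.1); 15% attrition (11.2); "a type I error of 0.05", two-sided (17.1).

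**Assumptions, because the documents give no figure.** Normal scores in SD units; baseline-to-post correlation r of 0.5 to 0.7; four cold losses before the first post-test (4/30 = 13%) and no hot losses; no true difference.

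1. *The plan's own size.* The protocol says the calculation was "based on a 2-tailed, two-way repeated measure ANOVA for the design". The 26 per group is reproduced by a two-sample t-test with an assumed standardised difference of 0.8, which has power 0.807. Adding 15% gives 26 × 1.15 = 29.9, so 30; dividing gives 26/0.85 = 30.6, so 31. With 30 hot and 26 cold scores, power at 0.8 is 0.835. Power is therefore not the main problem.

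2. *Bias of the unadjusted comparison.* When loss depends only on baseline, bias = r × s, where s is the upward shift in mean standardised baseline among the cold students who remain.
   - Loss unrelated to competence: s = 0, so bias = 0.
   - Odds of loss doubling per SD of lower baseline: s is about 0.1, so bias is 0.5 × 0.1 = 0.05 to 0.7 × 0.1 = 0.07 SD.
   - The four lowest at baseline lost: s is about 0.238, so bias is 0.5 × 0.238 = 0.12 to 0.7 × 0.238 = 0.17 SD.

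   Here weaker students leave, so the shift is toward cold. If stronger students leave, the sign reverses.

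3. *Type I error.* The standard error is √(1/26 + 1/30) = 0.268 SD. Biases of 0.05 and 0.07 are 0.19 and 0.26 standard errors, and simulation puts type I error near 5.5%. Biases of 0.12 and 0.17 are 0.45 and 0.63 standard errors, and simulation gives 8 to 10%. With loss unrelated to competence it stays at 5%.

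4. *Adjusting for baseline.* ANCOVA on the same students, with the same four missing, gives bias of about 0 and type I error of about 5% in both dependent cases. In theory the standard error falls by 1 − √(1 − r²), which is 13% at r = 0.5 and 29% at r = 0.7. In simulation it falls by about 12 to 27%.

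5. *What adjustment cannot do.* If the four lost are the lowest on the outcome itself, the unadjusted bias is about 0.24 SD with type I error of about 17%. Baseline adjustment does not remove bias of that kind.

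**The case against.** The strongest case against has four parts.

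- *Nothing says data are deleted after lost contact.* This stands. A reader might infer it because 14.1 promises non-deletion only to those who complete Phase 1. But that sentence opens on Phase 2, and its second mention of Phase 1 looks like a slip for Phase 2. The one removal rule stated, in 14.3, applies on request.
- *Section 14 does not create the no-show problem.* This also stands. A cold student who never returns has no post-test under any wording, and baseline adjustment removes baseline-dependent bias without touching Section 14. The wording of 14.3 matters for students who are present and willing but have refused one component.
- *A biased H1b is not shown.* Correct. A reader might infer that H1b becomes a completer comparison tilted toward cold. At the first post-test the t-test can use anyone with that score, so it is an available-case comparison. No passage ties loss to performance. The burden that 13.1 names is travel and scheduling, and the extra $25 comes only after the debrief and post-test. If both arms lose similar students, the bias is near zero.
- *The conflict with 6.3 is mild.* Partly right: declining a question is not the same as refusing a part of the study. The tension between 14.1 and 14.3 is clearer, and neither section says where the line falls.

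What survives is that 14.3 loses scores it need not lose, and that H1b has no protection against unequal loss although the baseline score is already collected.

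**Conclusion.** The point holds as a risk that is cheap to reduce. It is not a demonstrated bias. The refusal rule in 14.3 is broader than it needs to be and does not fit well with 14.1. The extra cold-arm visit before any post-test, with an unadjusted t-test and no missing-data rule, leaves H1b open to bias if loss differs by arm and relates to competence.

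For four cold losses and none in the hot arm, the plausible size runs from nothing to about 0.12 to 0.17 SD, with type I error from 5% to between 8 and 10%. A moderate dependence on baseline gives only 0.05 to 0.07 SD and about 5.5%. All of this rests on the assumed correlation and loss pattern, and the direction is unknown. The case for adjusting also rests on precision, which improves whether or not anyone is lost.

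**What to change.** 1. **Protocol 14.3.** State that refusing one component, such as the debriefing survey or one test, ends only that component. The remaining BLS assessments are still offered unless the student withdraws from the study. Align 14.1 and 6.3 with this.
2. **Protocol 17.1 and SAP.** Analyse students in their assigned arm using all available scores. Estimate H1b with adjustment for baseline BLS score, by ANCOVA or by a baseline-adjusted mixed model over both post-tests. Acknowledge that this does not remove bias from loss that depends on the outcome itself.
3. **Protocol 14.1.** Correct the retention sentence, and state that scores already collected are kept unless the student asks for removal.
4. **Reporting.** Give the number of missing BLS scores by arm and visit.

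The cost is wording in 14.1, 14.3, 17.1 and the SAP. No visit, student or measurement is added, and the rights to withdraw and to have data removed are unchanged. The small downside is handling a few partial records.

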| | 
6.1 Thoroughly describe the study design.
 
This study consists of two phases. Phase 1 will be a randomized controlled trial (RCT). Having a controlled group is the gold standard to measure the efficacy of an intervention (Polit & Beck, 2021). RCTs provide the most persuasive evidence on whether one variable has a causal influence on another. RCTs' main strength is the certainty with which causal links may be determined. Kolb's learning theory serves as the underpinning for this study (Kolb & Kolb, 2009; Kolb, 1984).
 
Manipulation: The researcher will do a cold debriefing (after one-day post-simulation) for undergraduate nursing students in the intervention group.
 
Control: The control group will do a hot debriefing (immediately after the simulation).
 
Randomization: The researcher will assign the participants to a control or experimental based on number generator.
 
Once participants complete Phase 1, we will record their progress on REDCap. If they chose to only participate in Phase 1, we will mark their status as "completed" on REDCap. If they expressed interest in Phase 2, we will randomly select 16 participants from the pool based on a number generator and update their status on REDCap for Phase 2.
 
Outcome: The study outcome is BLS competence level. The competence level will be measured AHA (2020) BLS competency Checklist. First, the control and experiment groups will complete a pre-test on BLS competence. Both groups will do a pre-test. After finishing
 |

TEMPLATE: RESEARCH PROTOCOL

| NUMBER | ACTIVE DATE | PAGE |
|---------|-------------|----------|
| HRP-503 | 02-04-2020 | 10 of 40 |

the pre-test, we will do the randomization process. Then the intervention group will receive (cold debriefing); the control group will have the (hot debriefing). Both groups will do the post-test immediately after the debriefing session and another post-test after 24 hours of the first post-test.

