For phase 2, we will do a qualitative descriptive design with focus groups interview. Themes relating to hot and cold debriefing will be generated using a focused qualitative interview technique. Focused interviews are loosely structured interviews in which the interviewer guides the participant through a set of questions (Polit & Beck, 2021). Throughout the guide, participants are encouraged to share their own experiences and discuss all topics freely. Researchers can obtain all necessary information utilizing this technique, and participants will have the capability to provide illustrations and explanations (Polit & Beck, 2021).

6.2 Detail the procedures being performed, specifically the interaction or intervention with human subjects and/or their identifiable information. Please be clear and concise and provide information relevant to the current study. For example, please be sure that what will be done for this research is explained and differentiated from activities that have already taken place or will be submitted for future review. Please note that details about recruitment and consent are asked in later questions.

Potential participants will access the REDCap link to answer the eligibility questions (1) if they are above 18 years of age and (2) if they are senior or third year undergraduate nursing students. If they are eligible, they will enter their demographic on REDCap. After that, The PI will assign the participants to a hot or cold debriefing group based on a number generator. Participants will do a baseline BLS competence where they will do a simulation experience related to the competence of BLS, which is conducted as part of the study design. There will be a scenario about a nurse taking care of their client at a hospital, and when the nurse enters the client's room to check on their client, they find that their client is unresponsive. Nursing students are expected to start the process of Basic Life support. Nursing students are expected in the simulation to check the client's

TEMPLATE: RESEARCH PROTOCOL

| NUMBER | ACTIVE DATE | PAGE |
|---------|-------------|----------|
| HRP-503 | 02-04-2020 | 11 of 40 |

responsiveness, activate the cardiopulmonary arrest code, begin cardiopulmonary resuscitation, and give 30 compressions and 2 breaths. They will attach an automated external defibrillator and follow the instruction of the machine. The total scenario will last up to 5 minutes.

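### Hypothesis 1b is tested by an unadjusted t-test that names neither of the two post-tests and leaves the collected baseline score unused

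*Protocol*

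**What the plan says.** Protocol section 6.1 sets two follow-up assessments in each arm: "Both groups will do the post-test immediately after the debriefing session and another post-test after 24 hours of the first post-test". Section 6.5 uses the same checklist (15 items, each scored 0 or 1) for baseline and both post-tests, so a baseline score on the outcome scale exists for every participant assessed.

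Hypothesis 1b in section 1.2 states that the cold arm will show greater competence and gives no time point. Section 5.1 defines the primary endpoint as completing phase 1, also without a time point. Section 17.1 gives the test: "For hypothesis 1b, an independent t-test will be used to find the differences between the two groups in the BLS competence level". The SAP repeats it: "An independent t-test was applied to examine differences in BLS competence levels between the two groups". Neither mentions a post-test, a covariate, a change score or a multiplicity rule.

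Pre-intervention scores enter only under hypothesis 1a, where section 17.1 says "the appropriate statistical analysis test will be the repeated measure ANOVA to find the difference between the experimental and control group". In the SAP the corresponding sentence is "A Paired t-test was used to determine the differences between the experimental and control groups before and after the intervention".

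The protocol describes the order of baseline and allocation in two ways. Section 6.1 says that after finishing "the pre-test, we will do the randomization process". Section 6.2 has participants enter demographics, then says "After that, The PI will assign the participants to a hot or cold debriefing group based on a number generator", and only then describes the baseline assessment.

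**The concern.** There are two gaps, and they differ in weight.

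The more important one is the open time point. The immediate post-test shows what a student can do straight after debriefing. The second shows what remains 24 hours later. These can differ, and hypothesis 1b could be supported by one and not the other. With no rule in either document, the choice could be made after the results are seen, and a reader of the report could not tell whether it was.

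The second gap is that the comparison discards the baseline score. A covariate measured on the same scale as the outcome usually explains some of the post-test variation, and using it narrows the interval for the hot-versus-cold difference. What is at stake is precision in a trial of 26 evaluable participants per arm.

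**Working it through.** **Inputs from the documents.** 26 per arm for analysis and 30 enrolled per arm (sections 3.1 and 17.1); two-sided 0.05; target power 80%; effect given as eta squared .25-.99 (section 17.1). **Assumptions, not in the documents:** the standardised difference d, the baseline-to-post-test correlation r, the correlation between the two post-tests, and independent observations.

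**The plan's own figure.** A two-sided independent t-test with d = 0.8 and n = 26 per arm has noncentrality d·√(n/2) = 0.8 × √13 = 2.884 on 50 df, hence power 80.7%. So 26 per arm matches an unadjusted two-group test at one time point with d = 0.8. It does not follow from eta squared .25. That gives f = √(.25/.75) = 0.577 and d = 2f = 1.155 as a two-group contrast, for which a one-way ANOVA needs 26 in total. I therefore show d = 0.8 as the main case and d = 1.155 as the case closest to the stated effect.

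**Open time point.** If a significant result at either post-test may count and the two were independent, the type I error would be 1 − 0.95² = 9.75%. A Monte Carlo check with no true difference (26 per arm, 200,000 trials per setting) gives:

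| Correlation between post-tests | Type I error, either may count |
|---|---|
| 0.3 | 9.6% |
| 0.5 | 9.1% |
| 0.7 | 8.4% |
| 0.9 | 7.1% |

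With one post-test named in advance it stays at 5%.

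**Baseline adjustment.** For ANCOVA the residual variance is multiplied by 1 − r², one degree of freedom is lost (49 df), and random baseline imbalance multiplies the variance by 1 + 1/(2n − 4) = 1 + 1/48. The noncentrality is d·√(n/2) / √[(1 − r²)(1 + 1/48)]. At d = 0.8 and r = 0.5 this is 2.884 / √(0.75 × 1.0208) = 2.884 / 0.875 = 3.296, hence power 89.8%. The 95% CI half-width in SD units is 2.009 × √(2/26) = 0.557 unadjusted; adjusted, it is multiplied by √[(1 − r²)(1 + 1/48)].

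| Analysis, 26 per arm | Power, d = 0.5 | Power, d = 0.8 | Power, d = 1.155 | CI half-width (SD) |
|---|---|---|---|---|
| t-test | 42.4% | 80.7% | 98.3% | 0.56 |
| ANCOVA, r = 0 | 41.7% | 79.9% | 98.1% | 0.56 |
| ANCOVA, r = 0.2 | 43.1% | 81.5% | 98.5% | 0.55 |
| ANCOVA, r = 0.3 | 45.0% | 83.5% | 98.9% | 0.54 |
| ANCOVA, r = 0.5 | 52.4% | 89.8% | 99.7% | 0.49 |
| ANCOVA, r = 0.7 | 68.8% | 97.5% | >99.9% | 0.40 |

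Without the imbalance factor, the d = 0.8 figures are 82.3, 84.2, 90.4 and 97.7% at r = 0.2, 0.3, 0.5 and 0.7. With all 30 per arm and d = 0.8, the t-test has 86% and ANCOVA 87, 89, 94 and 99% at the same four values of r.

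**The case against.** **The planned test is not wrong.** A reader might infer that ignoring baseline biases the comparison. It does not: at one fixed post-test, an unadjusted t-test after randomisation is valid if observations are independent. Section 6.2 leaves independence in doubt ("Another interaction with participants will be the debriefing experiences, where students will do a group debriefing"), but that affects the adjusted and unadjusted tests alike, and adjustment would not cure it. The power figures above are conditional on independence for the same reason.

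**The precision gain may be small.** This stands. The documents give neither r nor d = 0.8. Repeated testing on a 15-point checklist may reach a ceiling, which would make r low. If eta squared .25 is read as a two-group contrast, the t-test already has 98.3% power and at most 1.7 points can be gained. Taken alone, adjustment is an inexpensive improvement and not a necessity.

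**The repeated measures ANOVA already uses baseline.** Section 17.1 also bases the sample size on a two-way repeated measures ANOVA, so a group-by-time analysis may have been intended. But section 17.1 assigns that ANOVA to hypothesis 1a and gives 1b its own t-test, and the SAP lists only t-tests. It does not supply a baseline-adjusted test of 1b.

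**The different timing of the arms.** A reader might infer that the choice of post-test matters because the cold arm is tested about 24 hours later after the simulation than the hot arm. That offset is the same at both post-tests and is the intervention itself, so it does not separate them. What separates them is immediate performance against performance a day later.

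**The order conflict is mild.** Section 6.1 is explicit, whereas section 6.2 implies its order only by narrative sequence, and baseline precedes debriefing either way. It still needs settling before baseline becomes a covariate. The investigator assigns the groups (6.2) and may score the checklist (6.5), so knowing the allocation could affect the baseline score.

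**Conclusion.** The point holds in a limited form. Neither document fixes the post-test for hypothesis 1b. If either could count, the two-sided type I error would be about 7-10% for assumed between-test correlations of 0.9 to 0.3. This part alone justifies a change.

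Using baseline is an additional, conditional gain. At 26 per arm and d = 0.8 it is worth about 1-4 power points at r = 0.2-0.3 and 9-17 at r = 0.5-0.7, with a loss of under 1 point at r = 0. The CI half-width goes from 0.56 SD to between 0.55 and 0.40 SD for r = 0.2-0.7.

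A reader might also infer from the past tense of the SAP that a time point was picked to suit the results. The documents do not show this; they show only that nothing in them would have prevented it.

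**What to change.** In protocol section 17.1 and in the SAP:

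- Name one post-test for hypothesis 1b and make the other secondary.
- Analyse the named post-test by ANCOVA of total checklist score on group, with the baseline score as covariate. Report the adjusted difference in checklist items with its 95% CI.
- Reconcile sections 6.1 and 6.2 so that it is clear whether baseline is scored before allocation.

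If the analysis has already been done, report baseline-adjusted results for both post-tests beside the planned t-tests. State that the time point was not pre-specified, and whether baseline was scored before allocation.

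The cost is one model term in JMP and a few sentences, with no new data. The downside is one degree of freedom, and little gain if the correlation is low or the true effect is as large as eta squared .25.
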